8. RESEARCH QUESTION AND OBJECTIVES

The goal of this study is to investigate the risk of COPD exacerbations, community acquired pneumonia, and health care utilization in maintenance treatment naïve patients treated as first line therapy with Fixed Dose Combination (FDC) of Tiotropium + Olodaterol (Stiolto, 5/5 mcg), in comparison to maintenance treatment naïve patients treated with first line therapy, FDC of Fluticasone Furoate + Umeclidinium + Vilanterol (Trelegy, 100/62.5/25 mcg). Primary and Secondary analyses will be conducted for the total population and

Primary objective:

- To characterize the COPD patient population who are maintenance treatment naïve and initiated Trelegy or Stiolto as the first line therapy.
- To compare the effectiveness of Stiolto (new treatment initiation) with Trelegy (new treatment initiation) for time to the first COPD exacerbation (moderate/severe) in COPD patients who are maintenance treatment naïve.
- To compare COPD exacerbations following initiation of Stiolto (new treatment initiation) with initiation of Trelegy (new treatment initiation)

Secondary objectives:

- To compare the effectiveness of Stiolto (new treatment initiation) with Trelegy (new treatment initiation) for time to the first hospitalization of community acquired pneumonia in COPD patients who are maintenance treatment naïve.
- To assess differences between Stiolto vs Trelegy in, "all-cause" and "COPD and/or pneumonia-related", HCRU and HCRU cost (total population and sub-groups by care setting).

9. **RESEARCH METHODS**

9.1 STUDY DESIGN

This is a non-interventional study with existing data. It will be a retrospective, observational, non-interventional, new user design, real world study of Commercial Insurance and Medicare beneficiaries, using administrative claims data for the period of 15th September 2016 through 31st March 2020.

Patients initiating Stiolto, or Trelegy will be identified using pharmacy claims database). The date of the first prescription claim (on or after 15th September 2017) will be defined as the index date. Patients will be required to have a diagnosis of COPD (ICD-9-CM: 491.xx, 492.xx, 496.xx; ICD-10-CM: J41-J44) on two separate medical claims. Patients 40 years or older will be included in the study. Patients will be required to have continuous enrolment for 12 months prior to the index date. Patients will be excluded if they show any

Proprietary confidential information © 2022 Boehringer Ingelheim International GmbH or one or more of its affiliated companies

use of COPD maintenance medications (ICS, LABA or LAMA in any combination), during the baseline period of six months pre-index date. This will satisfy the criteria for being considered as treatment naive. Patients with two separate medical claims with a diagnosis of asthma, lung cancer, interstitial lung disease, or cystic fibrosis during the study period will be excluded. Using propensity score matching (PSM) technique, we will develop matched cohorts of patients between Stiolto initiators and Trelegy initiators. We will conduct 1:1 matching using nearest neighbour matching approach with a caliper of 0.2. Exacerbation will be defined as a COPD hospitalization (severe exacerbation) or Emergency Department (ED) visit (severe exacerbation) with COPD, or use of approved respiratory antibiotics (e.g., Azithromycin) \pm Oral CorticoSteroids (OCS) medications within \pm 7 days of the office/outpatient visit (moderate exacerbation) as the primary diagnosis. Multiple exacerbations occurring within 14 days of each other will be considered as a single exacerbation and will be per the higher severity. A schematic of the study design is presented below in Figure 1.

Boehringer Ingelheim Non-Interventional Study (NIS) Protocol BI Study Number 1237-0121

c38026921-01

Proprietary confidential information © 2022 Boehringer Ingelheim International GmbH or one or more of its affiliated companies

Figure 1 Study Design

Patients will be followed the index date to record time to first incidence of exacerbations, record time to first incident case of pneumonia, and HCRU. The analysis will be, "on treatment", analysis. Patients will be followed from the index date until the earliest of the first occurrence of outcome event, switch in index treatment (Stiolto or Trelegy), discontinuation of index treatment (Stiolto or Trelegy), the end of the study period, the end of continuous health plan eligibility, or (for main analyses) one year after index date. Hazard ratios and their 95% CI from proportional hazards models will be used to assess differences in the risk of COPD exacerbation and pneumonia.

Proprietary confidential information © 2022 Boehringer Ingelheim International GmbH or one or more of its affiliated companies

9.2 SETTING

We will utilize medical and pharmacy claim records for COPD patients included in the database (previously named database). This database contains administrative insurance data and enrolment information derived from approximately 150 million commercially insured and Medicare lives. This longitudinal database allows documentation and analysis of the patient journey from diagnosis to intervention and follow-up. It is nationally representative covering 90% of US hospitals and compliant with current HIPAA (Health Insurance Portability and Accountability Act) regulations.

9.2.1 Study sites

There are no specific trial sites in this study. We will utilize medical and pharmacy claim records for COPD patients included in the database (previously named database (previously named database contains administrative insurance data and enrolment information derived from approximately 150 million commercially insured and Medicare lives. This longitudinal database allows documentation and analysis of the patient journey from diagnosis to intervention and follow-up. It is nationally representative covering 90% of US hospitals and compliant with current HIPAA (Health Insurance Portability and Accountability Act) regulations.

9.2.2 Study Population

Patients initiating Stiolto, or Trelegy will be identified using pharmacy claims (database). The date of the first prescription claim (on or after 15th September 2017) will be defined as the index date. Patients will be required to have a diagnosis of COPD (ICD-9-CM: 491.xx, 492.xx, 496.xx; ICD-10-CM: J41-J44) on two separate medical claims. Patients 40 years or older will be included in the study. Patients will be required to have continuous enrolment for 12 months prior to the index date. Patients will be excluded if they show any use of COPD maintenance medications (ICS, LABA or LAMA in any combination), during the baseline period of six months pre-index date. This will satisfy the criteria for being considered as treatment naive. Patients with two separate medical claims with a diagnosis of asthma, lung cancer, interstitial lung disease, or cystic fibrosis during the study period will be excluded. Using propensity score matching (PSM) technique, we will develop matched cohorts of patients between Stiolto initiators and Trelegy initiators. We will conduct 1:1 matching using nearest neighbour matching approach with a caliper of 0.2. Exacerbation will be defined as a COPD hospitalization (severe exacerbation) or Emergency Department (ED) visit (severe exacerbation) with COPD, or use of approved respiratory antibiotics (e.g., Azithromycin) \pm Oral CorticoSteroids (OCS) medications within ± 7 days of the

Proprietary confidential information © 2022 Boehringer Ingelheim International GmbH or one or more of its affiliated companies

office/outpatient visit (moderate exacerbation) as the primary diagnosis. Multiple exacerbations occurring within 14 days of each other will be considered as a single exacerbation and will be per the higher severity.

Patients will be followed after the index date to record time to first incidence of exacerbations, record time to first incident case of pneumonia, and HCRU. The analysis will be, "on treatment", analysis. Patients will be followed from the index date until the earliest of the first occurrence of outcome event, switch in index treatment (Stiolto or Trelegy), discontinuation of index treatment (Stiolto or Trelegy), the end of the study period, the end of continuous health plan eligibility, or (for main analyses) one year after index date. Hazard ratios and their 95% CI from proportional hazards models will be used to assess differences in the risk of COPD exacerbation and pneumonia.

Inclusion Criteria:

- \geq 40 years of age as of the year of the index date
- At least one pharmacy claim for Stiolto Respimat or Trelegy Ellipta between 15 September 2017 and 31st March 2020.
 - For Stiolto Respimat users, the first pharmacy claim of FDC of Tiotropium + Olodaterol (5/5 mcg) will be defined as the index date.
 - For Trelegy Ellipta users, the first pharmacy claim of FDC of Fluticasone Furoate + Umeclidinium + Vilanterol (100/62.5/25 mcg), will be defined as the index date.
- Two medical claims (at least one claim on index date or before in the baseline period) with an ICD-9/10 diagnosis code(s) for COPD in any position during the study period (baseline ± post index date).
- At least one year of continuous medical and pharmacy health plan eligibility prior to the index date is required (to allow a baseline period for the covariates and characterizing the study population).

Exclusion Criteria:

- To increase the likelihood of a true diagnosis of COPD, we will exclude all patients with two medical claims of asthma, cystic fibrosis, lung cancer, or interstitial lung disease in any position on separate dates of service during the study period.
- To restrict the cohort to first line maintenance therapy of Stiolto Respimat or first line maintenance therapy of Trelegy Ellipta we will exclude; patients on LAMA. monotherapy; LABA monotherapy; ICS monotherapy; free or FDC of ICS+LABA, LAMA+LABA, ICS+LABA+LAMA therapy within six months prior to index date.
- Pharmacy claims for multiple index medications on the index date.
- Pharmacy claims for non-index COPD maintenance medications on the index date.

Proprietary confidential information © 2022 Boehringer Ingelheim International GmbH or one or more of its affiliated companies

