Population:	 Maintenance Treatment Naïve COPD patients using Stiolto vs. Trelegy. Exclusion Criteria: To increase the likelihood of a true diagnosis of COPD, we will exclude all patients with two medical claims of asthma, cystic fibrosis, lung cancer, or interstitial lung disease in any position on separate dates of service during the study period. To restrict the cohort to first line maintenance therapy of Stiolto Respimat or first line maintenance therapy of Trelegy Ellipta we will exclude; patients on LAMA. monotherapy; LABA monotherapy; ICS monotherapy; free or FDC of ICS+LABA, LAMA+LABA, ICS+LABA+LAMA therapy within six months prior to index date. Pharmacy claims for multiple index medications on the index date. 		
Variables:	Moderate and Severe COPD exacerbation, Pneumonia (time to and counts), HCRU for COPD and Pneumonia; both related and attributable costs.		

Name of company:			
Boehringer Ingelheim			
Name of finished medicinal product: Stiolto/Spiolto			
Name of active ingred Tiotropium bromide	dient: + Olodaterol		
Protocol date:	Study number:	Version/Revision:	Version/Revision date:
25 October 2021	1237.0121	1.0	N/A
Title of study:	Comparison of Exacerbation Risk and Health Outcomes in Maintenance Treatment Naïve COPD patients using Stiolto vs. Trelegy.		
Data sources:	We will utilize medical and pharmacy claim records for COPD patients included in the database (previously named This database contains administrative insurance data and enrolment information derived from approximately 150 million commercially insured and Medicare lives. This longitudinal database allows documentation and analysis of the patient journey from diagnosis to intervention and follow-up. It is nationally representative covering 90% of US hospitals and compliant with current HIPAA (Health Insurance Portability and Accountability Act) regulations.		
Study size:	\sim 3000 patients in each cohort are sufficient for \geq 80% power of		
Data analysis:	Summary measures will include standard descriptive statistics (e.g., mean, standard deviation, median and range for continuous variables; counts and percentages for categorical variables).		
Milestones:	Data collection will begin in Nov 2021, interim results will be available in Dec 2021, data collection will end in Dec 2021, and the final report will be completed and be made available in Jan 2022.		

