9.3.1 Exposures

Patients will be assigned to one of the following mutually exclusive study cohorts based on the index pharmacy claim: Stiolto Respimat or Trelegy Ellipta. Exposure measures will be based on pharmacy dispensing of the two medications under study, namely Stiolto Respimat or Trelegy Ellipta, over a follow-up period, beginning the index date and lasting up to one year from index date. Discontinuation for index medication will be defined as a gap in index medication of \geq 45 days (sensitivity analysis with \geq 30 days can be included) following the runout of days' supply (discontinuation date = runout prior to the gap in therapy). Switch in index medication will be defined as a pharmacy fill for \geq 30 consecutive days of a non-index maintenance medication (switch date = first date of the new treatment regimen). Switch includes any other change in use of index medication by active ingredient, inclusive of a change to a different combination therapy (ICS/LABA FDC, different LAMA/LABA or LAMA/LABA/ICS FDC) change from a FDC to a free form combination therapy with mono LAMA plus mono LABA, or mono ICS plus mono LABA, or mono LAMA plus mono LABA plus mono ICS or a change to a monotherapy.

Individuals in the study cohort will be followed from the index date until the earliest of the date of a switch in treatment, addition of an ICS for the Stiolto Respimat group, discontinuation of the index COPD maintenance treatment, the end of the study period, or the end of continuous health plan eligibility. Main analyses will be further limited to the first 12 months after index date, with sensitivity analyses considering all available data.

All patients will be required to be continuously enrolled in the health plan for a minimum of 12 months. The 12 months prior to and including the index date (index date – 364 through index date) will be used to assess baseline characteristics. The period starting the day after the index date, up to a maximum of 12 months duration (index date +1 through index date +365) will be used to assess exacerbation, pneumonia, HCRU and cost outcomes. Patients will be censored at the earliest of the following: discontinuation of the index medication (Stiolto or Trelegy), switch to a non-index medication, disenrollment from the health plan, 12-months following the index date, or the end of the study period.

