9.3.2 Outcomes

9.3.2.1 Primary Outcomes

The primary outcome event for effectiveness is time to first COPD exacerbation after cohort entry. The event is defined as follows:

- Severe exacerbation:
 - Hospitalization with a principal discharge diagnosis of COPD and/or
 - An emergency department (ED) visit with a discharge diagnosis of COPD
 - An inpatient admission or an ER visit with a diagnosis code for acute respiratory failure in the primary position and a COPD diagnosis code in any position
- Moderate exacerbation:
 - \circ An antibiotic for a respiratory condition dispensed \pm an OCS

Time to the first COPD exacerbation will be measured from index date until the occurrence of a hospitalization for COPD (severe exacerbation) or ED visit for COPD (severe exacerbation) or prescription of an antibiotic \pm an OCS on the same day (moderate exacerbation). Severe and moderate exacerbations were considered as a composite for main analyses. Sensitivity analyses will include stratification by exacerbation severity.

Exacerbations will be categorized as moderate or severe and a count of any (severe or moderate), severe, and moderate will be provided.

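### Sections 9.1 and 9.2.2 end follow-up at the first outcome event for exacerbations, pneumonia and HCRU alike; Section 9.3.1 has no such stop, and the planned counts and costs need follow-up beyond it

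*Combined protocol and SAP*

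**What the plan says.** Section 9.2.2 states that patients are followed after the index date "to record time to first incidence of exacerbations, record time to first incident case of pneumonia, and HCRU". Shortly afterwards it gives the end of that follow-up: "Patients will be followed from the index date until the earliest of the first occurrence of outcome event", followed by switch, discontinuation, end of study, end of eligibility and, for main analyses, one year. Section 9.1 uses the same rule. Neither section defines outcome event or limits this stop to particular analyses.

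Section 9.3.1 gives two further lists. The first begins "Individuals in the study cohort will be followed from the index date until the earliest of the date of a switch in treatment" and continues with addition of an ICS in the Stiolto group, discontinuation, end of study and end of eligibility. The second begins "Patients will be censored at the earliest of the following: discontinuation of the index medication" and continues with switch, disenrollment, 12 months and end of study. Neither contains an outcome event. Between them, the section sets index date +1 to index date +365 as the period that "will be used to assess exacerbation, pneumonia, HCRU and cost outcomes".

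Several planned outputs depend on which rule applies:
- The third primary objective (Section 8) compares exacerbations, and Section 9.3.2.1 says that "a count of any (severe or moderate), severe, and moderate will be provided".
- The abstract lists pneumonia both as a time to event and as counts.
- The exacerbation definition after Appendix 3 extends an episode when further qualifying events occur and classifies it by its most severe event.
- Section 9.7 annualizes cost as total cost divided by total follow-up patient-years in each cohort.

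**The concern.** The plan states two different ends of follow-up for the same outcomes, and nothing says which governs which. Section 9.2.2 names HCRU under the follow-up that stops at the outcome event, and Section 9.3.1 names HCRU under a window that does not. Two programmers could each follow a section of the protocol and derive different end dates. The code checking in Section 9.8 would have no single rule to check against.

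At stake are the exacerbation counts by severity, which serve a primary objective, and the secondary HCRU and cost results. Time to first pneumonia hospitalization is also at stake if outcome event is taken to mean any outcome.

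**Working it through.** The plan states no figure on this point, so there is none to reproduce. The check sets the literal 9.1/9.2.2 rule against the planned outputs and then illustrates its size.

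**Consequences of the literal rule**
- Exacerbation count: follow-up ends at the first event, so each patient's count is 0 or 1.
- Episodes: later qualifying events fall after follow-up has ended. A moderate event followed within 14 days by a hospitalization could not be upgraded to severe, as the episode rule requires.
- HCRU and cost: care after the event is not counted in patients who have an event.
- Pneumonia: if outcome event means any outcome, an exacerbation ends follow-up for pneumonia (and, formally, the reverse). If it means the outcome under study, this does not arise.
- Primary Cox analysis: its own first event ends time at risk there in any case, so that stop changes nothing.

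**Size, for illustration only**

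Assumptions, none of them from the documents: a constant rate L of 0.5 or 1.0 exacerbations per person-year, and otherwise complete follow-up of T = 1 or 0.5 year. The shorter T is included because the analysis is on-treatment and censors at discontinuation, switch and disenrollment.

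Mean count kept = 1 − exp(−LT), against LT in full. Share of person-time kept = (1 − exp(−LT)) / (LT).

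| L | T (years) | Full mean count | Mean count kept | Person-time kept | Person-time lost |
|---|---|---|---|---|---|
| 0.5 | 1 | 0.50 | 0.393 | 0.393/0.50 = 0.787 | 21% |
| 1.0 | 1 | 1.00 | 0.632 | 0.632/1.00 = 0.632 | 37% |
| 0.5 | 0.5 | 0.25 | 0.221 | 0.221/0.25 = 0.885 | 12% |
| 1.0 | 0.5 | 0.50 | 0.393 | 0.393/0.50 = 0.787 | 21% |

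Over a wider assumed range of 0.3 to 1.5 per person-year with T = 1, the loss is 14 to 48%.

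Under a constant rate, the share of events lost equals the share of person-time lost. If patients differ in their underlying rate (gamma frailty with variance 1, T = 1), the mean count kept is L/(1 + L). That is 0.333 at L = 0.5 and 0.500 at L = 1.0, so 33% and 50% of events are lost. Person-time kept is then ln(1 + L)/L = 0.811 and 0.693.

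**Effect on annualized rates**

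Section 9.7 divides by patient-years, and the stop shortens these as well.
- Constant rate, T = 1: 0.393/0.787 = 0.50 and 0.632/0.632 = 1.00. These are the untruncated rates.
- Frailty variance 1, T = 1: 0.333/0.811 = 0.411 and 0.500/0.693 = 0.721, below the true 0.5 and 1.0.

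Whether an annualized result moves therefore depends on assumptions that the documents do not supply.

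**The case against.** The strongest reply is that the rule is simply the usual time-to-event rule. In Section 9.2.2 it stands between a sentence about time to first exacerbation and first pneumonia and a sentence about hazard ratios. HCRU and cost accumulate, so a first occurrence has no natural meaning for them. Section 9.3.1 is the section that sets the window for cost, and it has no event stop. A literal stop would also leave the counts and multiple-event episodes with little content, so an analyst who reads the whole protocol is unlikely to cap counts at one.

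Most of this stands. The per-outcome reading is natural and probably intended, and it would truncate neither counts nor costs. It has to be inferred, however. HCRU is named under the same follow-up. The same sentence limits its one-year stop to main analyses but puts no limit on the event stop. Section 9.3.1 disagrees with it on its face.

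A reader might infer three stronger points that the documents do not support:
- That every patient's follow-up is cut short. Patients without an event are unaffected by this stop.
- That cost differences are biased toward no difference, because more expensive time is removed in the arm with more events. The denominator is truncated too, and under a constant rate the annualized event rate does not change. Any bias, and its direction, would depend on differences between patients, on cost after the event and on whether the event's own cost is counted.
- That 21 to 37% is an expected loss. It rests on an assumed rate and a full year on treatment.

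**Conclusion.** The contradiction is real and should be resolved before programming. Sections 9.1 and 9.2.2 state a stop that Section 9.3.1 omits, for overlapping outcomes. If programmed as written, that stop cannot deliver the exacerbation counts, the multiple-event episodes or HCRU and cost over the whole on-treatment window. The documents do not show that the sponsor intends this reading.

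The person-time losses of about 21 to 37% (full year) and 12 to 21% (six months) are conditional on the literal reading, on an assumed 0.5 to 1.0 events per person-year and on a constant rate. No direction of bias in annualized cost can be claimed.

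**What to change.** In Sections 9.1 and 9.2.2, state that the first event ends follow-up only in that outcome's own time-to-first-event analysis. State also that counts, rates, HCRU, costs and the other time-to-event outcomes continue to the Section 9.3.1 censoring date. Define outcome event separately for each analysis.

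Because this points to Section 9.3.1, reconcile its two lists at the same time so that there is one censoring date: only the first names addition of an ICS in the Stiolto group.

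The cost is one sentence in each of two sections and an alignment of the lists. No new data are needed, and the primary Cox model does not change.

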7. RATIONALE AND BACKGROUND

Chronic obstructive pulmonary disease (COPD) is a leading cause of morbidity and mortality throughout the world.¹ COPD has risen to become the third leading cause of death in the United States (US). ^{2,3} The Global Initiative for Chronic Obstructive Lung Disease (GOLD) 2020 report and the American Thoracic Society 2020 report recommends dual bronchodilator therapy (DBT) with long-acting muscarinic antagonists (LAMAs) plus long-acting beta2-agonists (LABAs) for patients with COPD who have persistent symptoms and/or exacerbations on LAMA or LABA monotherapy. ^{4,5} Consideration of escalation to triple therapy (TT; LAMA+LABA+inhaled corticosteroids [ICS]) is recommended in case of further exacerbation (\geq 2 moderate exacerbations or 1 severe exacerbation) and after assessing the risks/benefits. An important consideration is the trade-off between preventing exacerbations to restrict TT use further, to only patients who are likely to respond to ICS (such as \geq 2 moderate exacerbations or 1 severe exacerbation in the previous year, to those with asthma-COPD overlap or elevated blood eosinophils. ⁷

Page 17 of 47

c38026921-01

Proprietary confidential information © 2022 Boehringer Ingelheim International GmbH or one or more of its affiliated companies

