 - If the qualifying event is an ambulatory visit or an OCS or antibiotic dispensing, the start date is the earliest of the associated medical visit or medication dispensing date.

Episode End Date

- \circ If the qualifying event is a hospitalization: discharge date + 14 days
- \circ If the qualifying event is an ER visit: start date + 14 days
- If the qualifying event is an ambulatory visit or an OCS or antibiotic dispensing: Fthe latest of the medical visit or medication dispensing + 14 days
- If the Episode End Date is after the end of follow-up, then set an additional flag CENSORED=1.
- NOTE: Under this definition, it is possible for the runout of a medication to exceed the End Date.
- MULTIPLE EVENT EPISODES
- If another qualifying event occurs before the episode End Date, then the episode is extended. The date of the second event is used to reset the End Date per the definition above, using information from this second event. The process continues until a 14-day period with no exacerbation qualifying events occur. The End Date is set (as defined above).
- *Episode Length:* (End date Start date) + 1

Proprietary confidential information © 2022 Boehringer Ingelheim International GmbH or one or more of its affiliated companies

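### A moderate exacerbation has two stated dates, and one of them can place it after the treatment switch that ends follow-up

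*Combined protocol and SAP*

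**What the plan says.** Four parts of the combined protocol and SAP meet here.

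- **End of follow-up.** Sections 9.1 and 9.2.2 follow each patient to "the earliest of the first occurrence of outcome event, switch in index treatment (Stiolto or Trelegy"), discontinuation, end of study, end of eligibility or one year. Section 9.3.1 restates the list without the outcome event: "Patients will be censored at the earliest of the following: discontinuation of the index medication (Stiolto or Trelegy), switch to a non-index medication", and so on. An earlier sentence in 9.3.1 also ends follow-up at "addition of an ICS for the Stiolto Respimat group". Neither section says what happens when an event and a censoring reason share a date.
- **Date of a switch.** Section 9.3.1 defines a switch as a fill covering at least 30 "consecutive days of a non-index maintenance medication", with "switch date = first date of the new treatment regimen". There is no lag.
- **Date of the event.** Section 9.3.2.1 states: "Time to the first COPD exacerbation will be measured from index date until the occurrence of a hospitalization for COPD", or an ED visit for COPD, or the prescription of an antibiotic with or without a same-day OCS. For moderate events the clock therefore stops at the drug. In Appendix 3 (COPD Exacerbation Definition), for an event made up of an ambulatory visit and a dispensing, "the start date is the earliest of the associated medical visit or medication dispensing date".
- **Gap between visit and drug.** Section 9.3 accepts the pharmacy claim up to 7 days either side of the visit.

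The only rule in Appendix 3 for events near the end of follow-up flags an episode whose end date runs past it. It does not cover an event that starts on the censoring date.

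**The concern.** The primary outcome is time to first moderate or severe exacerbation, analysed on treatment. If a visit for a flare also leads to a change of maintenance inhaler, the event and the censoring date fall close together, and a few days decide whether the patient counts as an event or as censored. Here the plan has two stated dates for the same moderate event. One of them can move an exacerbation that began on the index drug to the far side of the censoring date.

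Such a loss would not be random. It would remove exacerbations that led to a treatment change. If that happens more often in one cohort, the hazard ratio shifts. Losing Stiolto events lowers the Stiolto-to-Trelegy HR, in favour of the sponsor's product.

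**Working it through.** The plan gives no figure of its own on this point, so the check has two parts: the dating rules side by side, then the size under assumed losses.

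**1. Dating check.** Day counts are illustrative. Follow-up is censored on the switch-fill day (9.3.1).

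| Visit | Switch fill | Antibiotic fill | Event date, 9.3.2.1 | Event date, Appendix 3 |
|---|---|---|---|---|
| 100 | 103 | 100 | 100: kept | 100: kept |
| 100 | 100 | 100 | 100: tie | 100: tie |
| 100 | 100 | 103 | 103: lost | 100: tie |
| 100 | 100 | 107 | 107: lost | 100: tie |
| 100 | 102 | 104 | 104: lost | 100: kept |

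- A tie is kept if the code tests event date ≤ censoring date, and lost if it tests <. The plan does not say which.
- The last three Appendix 3 entries assume that an antibiotic claim dated after the end of follow-up may still complete the event definition. The plan does not say so. If claims are cut at the censoring date, these events disappear under Appendix 3 too.
- A hospitalised event is dated at admission (Appendix 3), so an inhaler filled at or after discharge comes later and the event is kept. An ED event can at most tie, and only with a same-day switch fill.

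**2. Size.** Let fS and fT be the shares of first events recoded as censored in the Stiolto and Trelegy cohorts. Time at risk hardly changes, so

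HR observed = HR true × (1 − fS) / (1 − fT).

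Inputs:
- 3018 patients per cohort (9.5).
- HR of Stiolto relative to Trelegy (9.7.1).
- Two-sided 5% level, assumed from the 95% CI.
- Share p of patients with an observed first event: 20-40%, assumed.
- fS and fT: assumed; the documents give none.

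The chance of a significant result when the true HR is 1.00 uses E = 3018 × p × [(1 − fS) + (1 − fT)] events, z = √(E/4) × |ln HR|, and Φ(z − 1.96) + Φ(−z − 1.96).

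Worked case: fS = 2%, fT = 0, p = 30%.
- HR = 0.98.
- E = 3018 × 0.30 × 1.98 ≈ 1,793.
- z = √448.2 × 0.0202 ≈ 0.43.
- Chance ≈ 7.1%. The loss is 0.02 × 3018 × 0.30 ≈ 18 Stiolto events.

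| fS | fT | HR read when true HR is 1.00 | Chance of false significance, p = 20-40% |
|---|---|---|---|
| 1% | 0% | 0.99 | 5.3-5.7% |
| 2% | 1% | 0.98/0.99 = 0.99 | 5.4-5.7% |
| 2% | 0% | 0.98 | 6.4-7.8% |
| 5% | 1% | 0.95/0.99 = 0.96 | 11-17% |
| 5% | 0% | 0.95 | 14-24% |

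A simulation (1,000 replicates, 30% annual risk, on-treatment censoring, about 1,180 events before any loss) agreed: for 5% against 0% it gave HR 0.95 and 15% rejection. With the triggering events kept, it gave HR 1.00 and 4.9%. This confirms the arithmetic; it says nothing about which loss share is realistic.

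**The case against.** Much can be said on the other side.

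- **A tie is not a stated loss.** The usual coding counts an event on or before the censoring date, and 9.2.2 lists the outcome event first. This stands: the missing tie rule alone would be a missing detail. It does not rescue an antibiotic filled after the switch under 9.3.2.1, which is no tie.
- **Appendix 3 is the natural operational rule.** It is the more explicit text and refers back to 9.3.2.1. That is a good reason to adopt it, but 9.3.2.1 is the section that defines the primary time variable, and it says something else.
- **The sequence is unusual.** The patient must fill the new inhaler before the acute antibiotic. This stands and argues for a small effect.

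A reader might also infer more than the documents support:

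- *That this is the expected course for a Stiolto patient.* Section 7 says escalation to triple therapy "is recommended in case of further exacerbation", but it goes on to specify at least two moderate exacerbations or one severe. A first moderate event does not meet that unless earlier history counts, and a severe event that is hospitalised is dated at admission and is largely safe.
- *That the loss is one-sided.* The switch rule applies to both cohorts, and Appendix 2 lists roflumilast and methylxanthines among the maintenance drugs, so Trelegy patients can be censored this way too.
- *That the two rules give opposite answers for a same-day visit and switch.* There the contrast is lost against tied. It is lost against kept only when the visit precedes the switch.
- *That flares treated with an OCS alone are lost this way.* Under 9.3.2.1 a moderate event needs an antibiotic, so these are not events there at all. That is a separate conflict with 9.3.

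**Conclusion.** The concern holds in a limited form. Sections 9.3.2.1 and Appendix 3 give different dates for the same moderate exacerbation. Combined with censoring on the first day of a new regimen and a 7-day allowance for the drug claim, the 9.3.2.1 date discards an event whose visit was on or before the switch and whose antibiotic was filled after it. Under Appendix 3 the event is kept or tied, and the tie is left open.

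An excess loss in the Stiolto cohort is plausible, because ICS addition ends follow-up only there and Trelegy already contains all three drug classes. It would favour Stiolto. This is inferred, not shown.

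The size cannot be fixed from the documents, which give no step-up, same-day-fill or delayed-fill rates. At 1-2% of Stiolto events and none of Trelegy's, the HR moves to 0.98-0.99 and false significance stays at about 5-8%. Larger shifts are easy to compute: 10% against 1% gives 0.90/0.99 = 0.91. But nothing in the documents suggests that one in ten first Stiolto events meets all the conditions. The point merits correction because the rule can give a wrong result and the repair is nearly free, not because a large bias has been demonstrated.

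**What to change.** 1. In 9.3.2.1, use the Appendix 3 start date as the event date.
2. In 9.2.2 and 9.3.1, state that an exacerbation or pneumonia event with onset on or before the date of switch, ICS addition or discontinuation counts as an event, and takes precedence over censoring on the same day.
3. Allow claims up to 7 days after that date only to complete the definition of an event whose onset was on or before it.
4. Report, by cohort, the number of events on the switch date or within the 7 days before it. This shows whether the issue matters in these data.

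The cost is a few sentences and a few lines of code, with no new data. The small downside is that a few events treated just after a switch will be attributed to the index drug.
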